### 1.6. Selection of two antigenic E6 synthetic long peptides.

Previous clinical vaccination trials in patients with HPV16-induced lesions were performed with a mix of 13 overlapping SLP derived from HPV16 E6 and E7 oncoprotein sequences. We have selected the most immunodominant regions of the overlapping SLP set, based on extensive immunomonitoring studies using circulating lymphocytes obtained from healthy donors [10] to determine the naturally occurring HPV16 responses and from patients in the various clinical vaccination trials i.e. patients with end stage CxCa [34,41], with VIN lesions [17,18], with CIN lesions [42] as well as of tumor infiltrating lymphocytes (TILs) in patients with HPV16+ CxCa and OSCC [30,43,44]. Two SLP sequences were selected from the E6 protein namely E6 71-95 and E6 127-158 for which we found detectable T-cell

NL48274.000.14

Phase I Study: Hesppecta vaccination in HPV+ lesions

responses in 40-60% of the vaccinated patients and healthy donors. Both Th and CTL responses were found against these two peptide sequences. In addition, we used internet-based epitope prediction databases to screen these two sequences for potential T-cell epitopes presented in the various HLA molecules. The IEDB and SYFPEITHI databases were used to predict epitopes in peptides E6 71-95 and 127-158 for HLA class I and II alleles. In the table below the numbers of predicted HLA class I-binding and class II-binding epitopes are listed for the most frequently occurring HLA-alleles in the human population. Based on these findings we can expect that at least 50 - 75% of the patients that will be injected with a combined mixture of these two antigens will respond to vaccination with an HPV16-directed T-cell response.

|                        | E6 71-95 | E6 127-158 |
|------------------------|----------|------------|
| HLA-A*01               | 4        | 1          |
| HLA-A*02               | 3        | 2          |
| HLA-A*03               | 3        | 4          |
| HLA-A*11               | 3        | 4          |
| HLA-A*2402             | 8        | 2          |
| HLA-A*26               | 4        | 0          |
| HLA-B*0702             | 3        | 2          |
| HLA-B*0801             | 2        | 4          |
| HLA-B*15               | 2        | 0          |
| HLA-B*51               | 2        | 1          |
| 7 HLA-class II alleles | 12       | 13         |

### 1.7. Toxicity study

Both selected E6 SLP were conjugated with the above mentioned Amplivant® TLR2 ligand under GMP conditions. These conjugates have been tested in rabbits for general toxicity in same dosing groups as planned in this clinical study. The results of these experiments have been described in the investigator brochure (IB). No toxicity was observed.

### 1.8. Dendritic cell maturation by the two clinical conjugates

The Amplivant® as TLR-ligand in the two conjugated E6 SLP was able to induce maturation (activation) of both murine and human monocyte-derived DCs (moDCs). In both cases the DCs specifically produced the essential T-cell activating cytokine interleukin 12 (IL-12) upon stimulation with the conjugates. Also, essential co-stimulatory markers such as CD86, CD80 and CD83, as well as MHC class II molecules, were up-regulated on the cell surface of stimulated DCs. On the other hand, production of the anti-inflammatory cytokine IL-10 was almost undetectable upon stimulation.

NL48274.000.14

Phase I Study: Hespecta vaccination in HPV+ lesions

Peripheral blood mononuclear cells (PBMC) were also stimulated with the conjugates and the pro-inflammatory cytokine IL-1 $\beta$  could be measured in response to stimulation.

### 1.9. Human T-cell activation

Human HPV16-specific CD4+ or CD8+ T-cell clones, isolated from the TIL populations of CxCa patients, who were capable of spontaneously mounting a HPV16-specific T-cell response and of which it was known that they recognized an epitope within the two Amplivant®-conjugated SLPs, were used to analyze the quality of the conjugates. After exposure to conjugate-loaded DCs, both HPV16-specific CD4+ and CD8+ T-cell clones from these patients strongly proliferate and produce IFN $\gamma$ , showing that the conjugated SLPs are taken up by the DCs and efficiently processed and presented in both HLA class I and II. The CD8+ T-cell clone proliferated to a much greater extent in response to conjugate-loaded DCs compared to SLP-loaded DCs or DCs that were incubated with a mixture of TLR-ligand and SLP. Approximately 100-fold lower concentrations of conjugate were sufficient for the same level of CD8+ T-cell activation than free TLR-ligand mixed with SLP. The tested CD4+ T-cell clones proliferated to a similar extent to conjugate-loaded DCs as to SLP- or mixture-loaded DCs. These data show that the use of these conjugates has great advantages for stimulating CD8+ T-cell responses to the HPV16 E6 epitopes in the conjugates, whereas the conjugates have no disadvantages with respect to induction of CD4+ T-cell responses to epitopes in the conjugates. In addition, we determined whether the two clinical conjugates are effective in the stimulation of cancer patient-derived T-cells. Upon stimulation of freshly isolated TILs with the conjugated SLP, CD4+ TILs produced significantly more IL-2 than TILs stimulated with unconjugated SLP. In addition, CD4+ T-cells from a lymph node of a cervical cancer patient strongly produced both IFN $\gamma$  and IL-2 and displayed a more activated phenotype in response to stimulation with conjugated SLP. Taken together, these data indicate that the quantity and quality of T-cell responses, and especially the HPV16-specific CD8+ T-cell response, in cancer patients can be markedly enhanced by *ex vivo* stimulation with Amplivant®-conjugated SLPs.

### 1.10. Intradermal vaccination

The vaccine will be injected *i.d.*, thereby targeting the vaccine to a dense network of cutaneous DCs, among others Langerhans cells and dermal DC. Intradermal vaccination strategies for vaccination have been tested in many cancers [45,46,47] and have met with some clinical benefit [48,49]. It was shown before that an *i.d.* challenge with the HPV16 SLP injected at a dose of 10  $\mu$ g per peptide in healthy subjects is safe and results in the induction of an HPV16-specific T-cell response in at least 13 out of 19 injected subjects as reflected by the appearance of skin reactions, the migration of HPV16-specific T-cells into the skin and/or an increase in the number of circulating HPV16-specific CD4+ and CD8+ T cells [9]. The 10  $\mu$ g dose of non-conjugated SLP was also *i.d.* injected in CxCa patients but failed to induce a response [24], suggesting that the dose of the conjugated peptide should at least be tested at a higher dose. Together, this shows that already at low concentrations of antigen an *i.d.* vaccination can induce HPV16-specific T-cell responses in comparison to higher doses used for subcutaneous (*s.c.*) injection. The dose needed to establish a strong T-cell response in HPV16+

NL48274.000.14

Phase I Study: Hespecta vaccination in HPV+ lesions

---

cancer patients by reactions is unknown and therefore a dose finding study will be needed. The use of Amplivant®-conjugated SLPs will assumingly induce proper Th1/CTL polarization. I.d. vaccination instead of s.c. vaccination is warranted to allow omission of the Montanide oil-depot used so far for s.c. vaccine injection, because of the occasionally late (1 year) vaccine site reactions [42] and discomfort.

### **1.11. Summary**

Based on the literature data and our own experience we propose a phase I clinical study to determine the biological activity of a vaccine within the predefined dose range that is able to induce HPV16 E6-specific T-cell mediated immunity. In addition this study will report on the safety of this second generation HPV16 vaccine consisting of selected two long E6-derived peptides covering multiple potential CTL and Th epitopes both coupled to a TLR ligand in a group of patients screened after diagnosis and standard treatment for HPV16+ induced tumors and premalignant lesions..

NL48274.000.14

Phase I Study: Hespsecta vaccination in HPV+ lesions

---

## 2. OBJECTIVES

Primary objective:

- To determine the biological activity of Hespsecta that is able to induce HPV16 E6-specific T-cell immunity within a proposed dose escalation of 1, 5, 20 or 50 µg/peptide - conjugate in patients with HPV16+ tumors or premalignant lesions.

Secondary objective:

- To study safety of Hespsecta by collecting all AE's according to Common Terminology Criteria for Adverse Events v4.0 (CTCAE)

NL48274.000.14

Phase I Study: Hespsecta vaccination in HPV+ lesions

### 3. STUDY DESIGN

This single center phase I trial will determine the biological activity of Hespsecta within the proposed dose range that induces HPV16 E6-specific immunity. In addition, this study will evaluate toxicity of vaccination with Hespsecta. This translational dose escalation phase I trial will be performed in 4 dose groups (1, 5, 20 or 50 µg/peptide), each group consisting of 6 patients (see paragraph 4.4). Patients will receive i.d. injections three times with a fixed dose of Hespsecta at an interval of every three weeks. Patients diagnosed with HPV16+ (pre-)malignant lesions will be informed of this study. They will be included at least one month after the last standard treatment (for details see paragraph 4). Patients will be recruited at the LUMC, including referrals from other hospitals. The HPV type will be determined in tumor tissue by the department of pathology using standard operating procedures (SOPs). After obtaining informed consent, patients will be screened for eligibility in the study. Safety will be assessed during the study by collecting all AE according to the CTCAE version 4 (see paragraph 7.1). Venous blood samples at different time points will be obtained for immunomonitoring and clinical parameters for safety establishment. Immunological responses will be determined in isolated PBMCs of all vaccinated patients at the different time points (for details see paragraph 7). The decision to start enrolment at the next dose level will be made by assessing the safety after 4 out of 6 patients at the previous dose level have completed the first follow up visit after the third vaccination. The Principal Investigator (PI) will employ listings of individual patient data related to baseline characteristics, safety, and study medication administration for the patients necessary to assess per above before decision to start enrolment at the next dose level. The PI will assess information per above for relevant patients, summarize findings, and give a recommendation whether or not he endorses the start of enrolment at the next dose level. The summary and recommendation from the PI, including all necessary individual patient background material, should be reviewed and commented on by the Independent Data Monitoring Committee (IDMC) members. After having received the opinion of the IDMC, the PI can issue a written approval (or disapproval) regarding the start of enrolment at the next dose level. If in two or more patients CTCAE grade 3 or 4 treatment related toxicity occurs the dose escalation phase will be discontinued. If in the lowest dose group two patients experience CTCAE grade 3 or 4 treatment related toxicity, there is no safe dose and the study will be discontinued.

NL48274.000.14

Phase I Study: Hespsecta vaccination in HPV+ lesions

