**Intervention:** Patients first treated with curative intent for HPV16+ premalignant lesions or tumors will be vaccinated intradermally (i.d.) in four dose escalation groups (1, 5, 20 or 50 µg/peptide). Each dose group exists of 6 patients. The dose range is based on a 10-100 fold higher bioactivity of Amplivant® conjugated peptides in preclinical studies. The starting dose of this dose escalation trial is based on preclinical murine experiments showing that a dose of 1 µg per Amplivant® conjugated peptide resulted in no severe toxicity and a suboptimal immune response in that the magnitude of the immune response increased when mice were given a higher dose of vaccine. We reason that this provides the best scientific basis for the first dose to start with. As Amplivant® conjugated peptides are expected to induce T-cell responses more effectively compared to unconjugated peptides, the lowest dose known (50 µg per peptide) of unconjugated peptides able to induce T-cell responses is used as highest dose in this trial. From the starting dose an ascending dose range is proposed, evaluating four doses (1, 5, 20, 50 micrograms per peptide). Notably, the higher the dose the smaller the dose-fold increase between the doses (5, 4, 2.5 times), this should allow for maximal safety. Patients will be vaccinated three times with an interval of three weeks with a fixed dose of Hespsecta (i.e. no escalating dose within the patient). Vaccination will start with the i.d. injection of the lowest dose. The decision to start enrolment at the next dose level will be made by assessing the safety after 4 out of 6 patients at the previous dose level have completed the first follow up visit after the third vaccination. The Principal Investigator (PI) will employ listings of individual patient data related to baseline characteristics, safety, and study medication administration for the patients necessary to assess per above before decision to start enrolment at the next dose level. The PI will assess information per above for relevant patients, summarize findings, and give a recommendation whether or not he endorses the start of enrolment at the next dose level. The summary and recommendation from the PI, including all necessary individual patient background material, should be reviewed and commented on by the Independent Data Monitoring Committee (IDMC) members. After having received the opinion of the IDMC, the PI can issue a written approval (or disapproval) regarding the start of enrolment at the next dose level. If in two or more patients, grade 3 or 4 vaccine related toxicity occurs the dose escalation phase will be discontinued. If in the lowest dose group two patients experience grade 3 or 4 vaccine related toxicity, there is no safe dose and the study will be discontinued.

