### 7.2. Secondary study parameters/endpoints

Safety will be determined by the incidence rate at each dose level based on the following safety parameters: adverse events (AE) and serious (SAE), changes in hematology and chemistry values, including those associated with hepatic and renal function, and assessment of physical examinations, vital signs and performance status using NCI-CTCAE version 4.0

[figure not shown]
([http://ctep.cancer.gov/protocolDevelopment/electronic\\_applications/ctc.htm#ctc\\_40](http://ctep.cancer.gov/protocolDevelopment/electronic_applications/ctc.htm#ctc_40)).

NL48274.000.14

Phase I Study: Hespsecta vaccination in HPV+ lesions

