## 8. SAFETY REPORTING

### 8.1. Section 10 WMO event

In accordance to section 10, subsection 1, of the WMO, the investigator will inform the subjects and the reviewing CCMO if anything occurs, on the basis of which it appears that the disadvantages of participation may be significantly greater than was foreseen in the research proposal. The study will be suspended pending further review by the CCMO, except insofar as suspension would jeopardize the subjects' health. The investigator will take care that all subjects are kept informed.

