#### 8.2.2. Serious adverse events (SAEs)

A SAE is any untoward medical occurrence or effect that at any dose:

- results in death;
- is life threatening (at the time of the event);
- requires hospitalization or prolongation of existing inpatients' hospitalization;
- results in persistent or significant disability or incapacity;
- is a congenital anomaly or birth defect;
- any other important medical event that may not result in death, be life threatening, or require hospitalization, may be considered a serious adverse experience when, based upon appropriate medical judgment, the event may jeopardize the subject or may require an intervention to prevent one of the outcomes listed above.

The sponsor will report a SAE through the web portal *ToetsingOnline* to the CCMO that approved the protocol, within 15 calendar days after the sponsor has first knowledge of the SAE.

A SAE that result in death or are life threatening should be reported expedited. The expedited reporting will occur not later than 7 calendar days after the responsible investigator has first knowledge of the SAE. This is for a preliminary report with another 8 days for completion of the report.

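### Both preset toxicity rules count only related grade 3 or 4 events, so a related event recorded only as fatal adds nothing to the count

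*Protocol*

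**What the plan says.** The protocol has two numeric toxicity rules, each stated in Section 3 and again in the synopsis under Intervention.

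- Escalation stop. Section 3: "If in two or more patients CTCAE grade 3 or 4 treatment related toxicity occurs the dose escalation phase will be discontinued". Synopsis: "If in two or more patients, grade 3 or 4 vaccine related toxicity occurs the dose escalation phase will be discontinued".
- Lowest-dose rule, which ends the study. Section 3: "If in the lowest dose group two patients experience CTCAE grade 3 or 4 treatment related toxicity, there is no safe dose". Synopsis: "If in the lowest dose group two patients experience grade 3 or 4 vaccine related toxicity, there is no safe dose".

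Section 7.2 names the grading scale ("vital signs and performance status using NCI-CTCAE version 4.0") but the protocol does not print it. Section 8.2.2 treats death as an outcome in its own right: it is the first seriousness criterion and a ground for faster reporting ("A SAE that result in death or are life threatening should be reported expedited"). Neither that section nor any other links death to the count used by the two rules.

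**The concern.** A stopping rule should be at least as sensitive to a worse event as to a milder one. These rules are not. Because the range has an upper limit, replacing a related grade 3 event with a related fatal one lowers the count.

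This is a first-in-human study, and the lowest-dose rule is the one that decides whether any dose is regarded as safe. On the literal wording, two related grade 3 events in that group would lead to that conclusion, while two related deaths recorded only as fatal would not. The mixed case, one death and one grade 3 event in different patients, also falls short.

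**Working it through.** **Inputs from the protocol**

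- Threshold: 2 patients, for both rules (Section 3 and synopsis).
- Grades counted: related grade 3 or 4 (the same four statements).
- Group size: 6 patients in each of 4 dose groups (Section 3). This reproduces the stated total: 4 × 6 = 24. The total is unaffected by this point.
- The protocol states no operating characteristic for the toxicity rules and no expected rate of related severe or fatal events.

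**Contribution of one patient to the count**

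| Patient's related toxicity | As written | If fatal events count |
|---|---|---|
| Non-fatal grade 3 or 4 | 1 | 1 |
| Recorded only as fatal | 0 | 1 |
| Death, with a related grade 3 or 4 toxicity also recorded | 1 | 1 |

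The third row matters for scope. A death in a patient who already has a recorded related grade 3 or 4 toxicity is captured through that toxicity and is not part of this point.

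**Rule outcome: count = sum of contributions, met if count ≥ 2**

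| Two patients in the lowest-dose group, unless stated | As written | If fatal events count |
|---|---|---|
| Both non-fatal grade 3 or 4 | 1 + 1 = 2, met | 1 + 1 = 2, met |
| One fatal-only, one non-fatal grade 3 or 4 | 0 + 1 = 1, not met | 1 + 1 = 2, met |
| Both fatal-only | 0 + 0 = 0, not met | 1 + 1 = 2, met |
| A single fatal-only event and no other patient | 0, not met | 1, not met |

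The wordings differ only when at least one of the counted patients has a fatal-only record and a second qualifying patient exists. As written, no number of fatal-only events meets the rule: six out of six would still give 0. The same arithmetic applies to the escalation stop, which has the same threshold and the same grades.

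These are counts under the rule, not likelihoods. Any probability would need assumed rates of related death, and the conclusion does not depend on one.

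**The case against.** The case for leaving the text alone has four parts.

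**Other provisions would act.** Section 8.1 applies if "it appears that the disadvantages of participation may be significantly greater than was foreseen in the research proposal", and the consequence is firm: "The study will be suspended pending further review by the CCMO", except where suspension would itself endanger subjects. Section 10.3 reports that adverse events with the earlier vaccine generally stayed at grade 2 or below, so one related death would almost certainly meet that bar. Section 7.8 allows termination for safety. Each escalation needs the principal investigator's written approval after committee review, and Section 8.5 requires the committee's approval too. This stands, and it is why the practical risk is small. But these routes start from a judgement. They do not alter the count and they do not produce the preset conclusion about the lowest dose.

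**A death would usually pass through grade 3 or 4.** Where that is recorded it counts, and the case is excluded here. A rapid event may be recorded only by its final outcome, however. The protocol itself prepares for acute anaphylaxis (Section 5.3). How often this would happen is unknown.

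**The scale is not printed.** That a fatal event lies above grade 4 comes from CTCAE v4.0, which the protocol adopts but does not reproduce. This dependence is real. The scale is the protocol's own standard, though, and the text alone shows death handled as a separate outcome that is never tied to the count.

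**Correction changes little.** A single related death leaves the rule unmet under either wording, and the study would probably be suspended before a second qualifying event. That limits the weight of the point. It does not make the written threshold right.

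**Conclusion.** The point holds. Both rules, in all four statements, give the wrong count when a related event is recorded only as fatal: 0 instead of 2 for two such events, and 1 instead of 2 for one such event with one grade 3 or 4 event in another patient. In both cases the rule is not met when it should be.

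The conclusion assumes a literal reading of the range and the CTCAE v4.0 convention that a fatal event is grade 5. If the authors meant grade 3 or higher, the correction only records that intent. The defect is confined to the upper limit of the range. It does not mean that a death would go unreviewed. It should be corrected because it is a safety threshold in a first-in-human trial, but it does not undermine the design.

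**What to change.** In both rules, in Section 3 and in the synopsis, replace the grade range with: grade 3 or higher, including fatal events. The related-toxicity condition and the threshold of two patients stay as they are. A single related death then counts as one and is still dealt with through Section 8.1, the sponsor and the data monitoring committee.

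The cost is four phrase replacements, two in each place. Sample size, endpoints and analysis do not change.

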## 4. STUDY POPULATION

### 4.1. Population (base)

Only in a minority of persons, HPV16 infection persists and subsequently (pre)malignant lesions develop. It is unknown in which persons the virus will be eradicated and in whom it will persist [6]. It is generally thought that immune related factors determine which persons clear and do not clear HPV16 infections [6,50]. As the targeted population of this therapeutic vaccine consists of patients with HPV16+ tumors or premalignant lesions, this vaccine should be tested in patients whose primary HPV infection has not been cleared. Previous experience showed that the vaccine-induced immune response differs between patients with pre-malignant lesions who have cleared their lesions [17,18,32] and patients with HPV16+ recurrent or metastatic cervical cancer. The latter patients showed much weaker vaccine-induced immune responses and in contrast to VIN patients with robust vaccine-induced immune responses did not show clinical benefit [41]. They showed not only a weaker immune response than successfully vaccinated VIN patients, but also to patients with high-grade premalignant lesions who have been successfully vaccinated. Notably, similar spontaneous responses against the HPV16 oncoproteins were observed in healthy individuals who have successfully cleared the virus [10]. Patients with premalignant lesions (CIN1-3, VIN3) had more side effects after vaccination with the first generation of Montanide emulsion SLP vaccine which emphasizes the need for new vaccine formulation [51]. As it is not possible to distinguish healthy individuals who are able to eliminate HPV16 from those who are not, it has been decided to perform this study in patients who are candidate for the improved second generation Hespsecta vaccine, i.e. either suffering from a HPV16+ premalignant lesion or a non-metastatic HPV16+ malignancy for which they have received the standard (curative intent) treatment. Premalignant lesions associated with HPV16 consist of vulval (VIN), cervical (CIN), anal (AIN) and Vaginal intraepithelial neoplasia (VAIN). HPV16+ malignant tumors can arise in the cervix, vulva, vagina, penis, anus and areas of the head and neck. A total of 24 eligible adult males or females in good clinical condition will be included in this trial.

